7.5 SECONDARY ENDPOINTS

All secondary efficacy endpoints in trial Part 1 will be considered exploratory in nature. All p-values presented for the secondary endpoints will be considered nominal in nature and no adjustment for multiplicity will be made.

7.5.1 Key secondary endpoint

This section is not applicable as no key secondary endpoint has been specified in the protocol for Part 1.

7.5.2 (Other) Secondary endpoints

Secondary continuous endpoint

From CTP Section 7.3.3:

For both trial parts, the change from baseline of IBDQ scores at Week 12 will be analysed based on the m-RS. It will be analyzed using a restricted maximum likelihood (REML) based repeated measures approach. The model will include fixed, categorical effects of treatment, visit and treatment by visit interaction, and stratification factors (prior biologic use and corticosteroid use), as well as the continuous, fixed covariates of baseline and baseline by visit interaction. An unstructured covariance structure will be used to model the within patient measurements. The Kenward- Roger approximation will be used to estimate denominator degrees of freedom. The primary treatment comparison will be the contrast between treatments after 12 weeks of treatments. For Part 1 of the trial, if model convergence issues occur due to inclusion of strata in the model, these terms may be dropped and separately evaluated.

For the IBDQ overall score, adjusted mean changes (and standard error) from baseline to Week 12 will be calculated for each treatment on the m-RS using the model described above. The adjusted mean (and 95% confidence interval) differences in change from baseline between each BI group and the placebo group will be calculated. The calculation of IBDQ overall score and handling of missing item data are further described in [Section 9.2.7](#). The analysis will be repeated for each domain score of the IBDQ.

SAS code for the above model will be based on the following structure:

```
PROC MIXED DATA=alldat cl method=reml order=formatted;  
  CLASS ptno trt stratum visit;  
  MODEL ept = stratum visit*trt base*visit / ddfm=kr s CL;  
  REPEATED visit / subject= subject type=un r rcorr;
```

```
LSMEANS visit*trt / pdiff=all om cl alpha=0.05 slice=tptno;  
RUN;
```

For handling of non-convergence, please refer to [Section 9.5](#). Patients will be analyzed according to the stratum as indicated on the eCRF.

Graphical displays of the adjusted means and 95% confidence intervals, for both the overall IBDQ score as well as per domain over time by treatment, will also be presented. Such displays will also be created for the difference of each treatment group to placebo.

The IBDQ overall score and its change from baseline, both overall and per domain, will be descriptively summarized for the m-RS by visit as a continuous variable based on the observed cases without imputation (OC).

Sensitivity analysis will be further performed on change from baseline of IBDQ overall score using multiple imputation approach. The missing data of IBDQ overall score will firstly be imputed via the multiple imputation approach, as described in [Section 6.6.2](#). The REML-MMRM will then be applied on the completed data after imputation.

Secondary binary endpoints

From CTP Section 7.3.3:

Part 1 – proof of clinical concept

If considered appropriate, a MCPMod approach may also be applied to selected secondary endpoints on Part 1 of the trial.

For each secondary binary endpoint, unadjusted absolute risk differences at Week 12 between the BI 655130 arms and the placebo group will be provided along with the corresponding 95% confidence intervals. A logistic regression model may also be performed on the RS using the approach as described above for the further analyses on the primary endpoint of Part 1 of the trial.

The analysis of secondary endpoints, per the approaches described above, will be done on the RS. With regards to the handling of missing data, NRI is the primary imputation technique.

The primary analysis MCPMod approach as described for the primary endpoint will be applied to clinical response and to endoscopic improvement only.

As defined for the primary endpoint, the method to provide a confidence interval for unadjusted risk differences is derived from the Wilson method by Newcombe ([14](#)).

Graphical displays of the proportion of patients who achieve a response on the applicable secondary binary endpoint (including 95% confidence interval), as well the risk difference vs. placebo, by treatment will also be presented.

[figure not shown]
[figure not shown]

Table 7.5.2: 1 Summary of analysis for secondary endpoints

Analysis & Endpoints	Analysis set	Imputation Approach	Analysis model
Secondary Binary endpoints			
- Clinical response at Week 12			
- Endoscopic improvement at Week 12			
Planned Analysis in CTP-1	RS	NRI	Unadjusted absolute risk

Note:

For MCP-Mod approach, best fitting model is used and no covariates adjustment is applied, unless otherwise specified.

Standard approach of SFS/RBS calculation (see [Section 9.2.1](#)) is applied unless otherwise specified.

For explanation of the different approaches with regard to missing data see [Section 6.6](#).

[figure not shown]
NRI = No Response Imputation

[figure not shown]
MI = Multiple Imputation

[figure not shown]
OC = observed cases

[figure not shown]
REML-MMRM = restricted maximum likelihood based mixed effect model with repeated measurement (* the missing data will be handled by MMRM model under MAR assumption)

[figure not shown]
A forest plot which displays the unadjusted risk differences versus placebo (and corresponding 95% confidence intervals) will be produced for the different analysis approaches in a single display. A separate display will be used to illustrate the subgroup effects on the applicable secondary endpoint.

7.6.4 Use of rescue medication

Frequency of use of rescue treatment (see [Section 5.4.5](#)) from randomization up to (and before) the Week 12/Visit 6 primary endpoint will be summarized with the number and percentage of patients by preferred name for the RS.

A separate presentation of the number and percentage of patients who had any change in the dose of background medication, by reason of dose change, from randomization up to (and before) the Week 12/Visit 6 primary endpoint will also be presented.

A Kaplan-Meier analysis of the time to first use of rescue medication (as defined in [Section 5.4.5](#)) will be presented. If no rescue medication was taken, then time will be censored as described in [Section 5.4.5](#).

7.7 EXTENT OF EXPOSURE

The number of subjects who received a dose of trial drug will be tabulated. The duration of infusion [in minutes] and the amount of treatment received [mg] (actual and weight based) will be summarised by descriptive statistics (N, mean, SD, minimum, Q1, median, Q3, maximum) per visit and overall. The total duration of exposure (days), defined as the date of start of the first infusion to date of end of the last infusion + 1 day, will also be displayed.

7.8 SAFETY ANALYSIS

All safety analyses will be performed based on the SAF following BI standards. No hypothesis testing is planned.

The primary safety analysis will be done based on data through the first 12 weeks of treatment at the time of the second interim database snapshot, which is consistent with the timing of the primary efficacy analysis per CTP. Further analysis, once the trial is complete and has final database lock, will also be done whereby selected summaries which include all safety data up to end of the REP will be produced.

7.8.1 Adverse events

AEs will be coded with the most recent version of MedDRA. Patients will be analysed according to the actual treatment received.

The exposure adjusted incidence rate (per 100 subject years) of a selected treatment emergent adverse event is defined as the number of subjects experiencing the adverse event per treatment group during time at risk divided by the total time of subjects at risk in that treatment group to contribute the event to the analysis multiplied by 100 (per 100 subject years), where:

$$\text{Time at risk [subject years]} = (\text{date of onset of TEAE} - \text{study drug start date} + 1) / 365.25$$

If, for a subject, the selected treatment emergent adverse event (TEAE) didn't occur then the time at risk will be censored at the minimum of either (date of death, [for patients who were not dosed in the extension trial] last contact date per EoS page, [for patients who were dosed in the extension trial] date of first dose in extension trial – 1 day, randomized drug stop date + 112 days, minimum of (analysis cut-off date, day 99) [if applicable, i.e. for primary efficacy and safety analysis at week 12]). For each selected treatment emergent AE, the exposure adjusted incidence rate will be calculated as:

$$\text{Incidence rate [1/100 Subject years (pt-yrs)]} = 100 * \text{number of subjects with AE} / \text{Total AE-specific time at risk [subject years]}.$$

The analyses of AEs will be descriptive in nature. All analyses of AEs will be based on the exposure adjusted incidence rates (per 100 subject years) as well as the number of patients with AEs, and not on the number of AEs. System organ classes (if applicable) will be sorted according to the standard sort order specified by the EMA. Preferred terms (if applicable) will be sorted by total frequency (within system organ class) across all treatment arms, or, if a total column across all arms is not foreseen in the table, by total frequency (within system organ class) within the BI arm.

For details on summarization of AE data, please refer to "Handling and summarization of adverse event data for clinical trial reports and integrated summaries" (16) and "Handling of missing and incomplete AE dates" (7).

The analysis of AEs will be based on the concept of treatment emergent AEs. Since only the start date of an AE is collected (without start time), any AE occurrence on the same day as the first BI 655130 administration will be assigned to the on-treatment period. For patients who enrol and are dosed in the extension trial, any AE which occurs up to one day prior to this first dose of extension trial medication will also be assigned to the on-treatment period in this trial.

An overall summary of AEs will be presented by treatment. This overall summary will include summary statistics for the class of other significant AEs according to sponsor definition based on ICH E3 and for the class of AESIs.

The following are considered as AESIs (refer to CTP section 5.2.6.1):

- Systemic hypersensitivity including infusion reaction and anaphylactic reaction
- Severe infections (according to RCTC grading)
- Opportunistic and mycobacterium tuberculosis infections
- Hepatic injury

A hepatic injury is defined by the following alterations of hepatic laboratory parameters:

a. ALT or AST >5x ULN

b. *ALT or AST >3x ULN with the appearance of fatigue, nausea, vomiting, right upper quadrant pain or tenderness, fever, rash, and/or eosinophilia (> 5%)*

c. *AST and/or ALT \geq 3 fold ULN combined with an elevation of total bilirubin \geq 2 fold ULN measured in the same blood draw sample*

The investigator identified AESI will be captured from the eCRF and reported in the “Investigator reported AESI” table. In addition, user defined adverse event concepts (UDAEC) identified through specific search criteria will be reported separately (see Table 7.8.1: 1).

Table 7.8.1: 1 Project MEDDRA search criteria for User Defined Adverse Events Concepts

UDAEC	Categories
Infusion/Systemic hypersensitivity reactions including anaphylactic reactions	Narrow SMQ “Anaphylactic reaction” Narrow SMQ “Angioedema” Narrow SMQ “Hypersensitivity”
Severe infections (according to RCTC grading)	SOC Infections and infestations of at least severe RCTC grade, by HLGT
Opportunistic and mycobacterium tuberculosis infections	BIcMQ “Infections”: Narrow sub-search 8 “Opportunistic infections including Tuberculosis related terms”
Tuberculosis related terms	BIcMQ “Infections”: Narrow sub-search 8.2 “Tuberculosis related terms” HLT “Tuberculosis infections”
Malignant tumours	(SMQ “Malignancies” – not for display) (Sub-SMQ “Malignant or unspecified tumours” – not for display) Narrow Sub-SMQ “Malignant tumours” Sub-SMQ “Haematological malignant tumours” Sub-SMQ “Non-Haematological malignant tumours”

Based on the specification provided in ICH E3 (17), the sponsor has defined AEs which are to be classified as ‘other significant’. For the current trial, these will include those non-serious AEs which were reported with ‘action taken = Drug Withdrawn’ or ‘action taken = Dose Reduced’.

The exposure-adjusted incidence rate and frequency of patients with AEs will be summarised by treatment, primary system organ class and preferred term. AEs which were considered by the investigator to be drug related will be summarised separately. Separate tables will also be provided for patients with SAEs, patients with drug-related AEs, patients with investigator-reported AESIs, patients with AE leading to discontinuation of the trial, patients with other significant AEs and User-defined Adverse Event Concepts (UDAEC) (see [Table 7.8.1: 1](#)). AEs will also be summarized by maximum intensity based on the RCTC measure (see [Section 5.4.1](#)).

For disclosure of AE data on ClinicalTrials.gov, the frequency of patients with non-serious AEs occurring with an incidence of greater than 5% (in preferred terms) will be summarised by treatment, primary system organ class and preferred term. The frequency of patients with SAEs will also be summarised.

For disclosure of AE data in the EudraCT register, the frequency of non-serious AEs with an incidence of greater than 5 % (in preferred terms) and the frequency of SAEs will be summarised.

7.8.2 **Laboratory data**

The analyses of laboratory data will be descriptive in nature and will be based on BI standards (18). Note that data from the central laboratory will be used for all displays described below, unless otherwise specified.

For continuous safety laboratory parameters, normalized values will be derived. Normalisation means transformation to a standard unit and to a standard reference range. The process of normalisation, handling of repeat values at the same visit for by-visit displays, as well as standard analyses for safety laboratory data are described in the BI guidance for the Display and Analysis of Laboratory Data (18). All analyses considering multiple times of the ULN (as described below) will be based on standardized and not normalized values. For continuous safety laboratory parameters, differences to baseline will be calculated.

Only patients with at least one available post-baseline value will be included in the analysis of an individual laboratory parameter. All individual laboratory data will be listed. Values outside the reference range will be flagged.

Descriptive statistics of laboratory values over time and for the difference from baseline (see [Section 6.7](#)) will be based upon normalized values and provided by visit, including the last value on treatment, the minimum value on treatment and maximum value on treatment. Graphical displays via box plots will be produced for the change from baseline, over time, for each continuous laboratory endpoint.

Laboratory values will be compared to their reference ranges; shift tables will be provided for the number of patients with a specific RCTC grade at baseline versus the grade at the last measurement on treatment, as well as the worst grade on treatment. These analyses will be based on standardized laboratory values.

Potentially clinically significant abnormalities will be identified based on BI standard rules which are based on normalized converted lab values, i.e. using SI units. These rules will be listed in the SDL appendix of the CTR. Frequency tables will summarize the number of patients with potentially clinically significant abnormalities. Patients having an abnormal lab value at baseline will be presented separately. A separate listing will present potentially clinically significant abnormal lab values; for each functional lab group all patient's lab values will be listed, if there exists at least one lab value with clinically significant abnormality within the group.

The frequency of patients with AST or ALT elevations $\geq 3xULN$, $\geq 5xULN$, $\geq 10xULN$, and $\geq 20xULN$ will be displayed based on standardized laboratory values. To support analyses of liver related adverse drug effects, the frequency of patients with AST and/or ALT $\geq 3xULN$ combined with a total bilirubin $\geq 2xULN$ in a 30 day period after AST/ALT elevation will be displayed, stratified by alkaline phosphatase $< 2xULN$ and $\geq 2xULN$ (a patient can potentially be in both alkaline phosphatase strata in case of multiple AST/ALT and bilirubin elevations). The start of the 30 day time span is triggered by each liver enzyme elevation above the defined thresholds. This analysis will be based on standardized laboratory values. A graphical analysis of the ALT and total bilirubin during the on-treatment period will also be performed; the so called eDISH plot. In the graph, for each subject, the peak total bilirubin is presented as a fold increase over the ULN against the peak ALT as a fold increase over the ULN, on a log₁₀ scale. The measurements displayed for total bilirubin and ALT may, or may not, occur on the same date. Two reference lines, 2xULN for total bilirubin and 3xULN for ALT, are drawn onto the graph in order to divide the plane into four quadrants. Normal cases are in the lower left quadrant, potential DILI cases are in the upper right quadrant (Hy's Law quadrant), while the lower right quadrant is known as the Temple's corollary range (ALT $\geq 3xULN$ and total bilirubin $< 2xULN$).

An additional display will be produced for the frequency of patients with an elevation of the ALT or AST > 3 -fold ULN and with the appearance of one or more of the following TEAE: fatigue, nausea, vomiting, right upper quadrant pain or tenderness, fever, rash, and/or eosinophilia ($>5\%$). An occurrence is flagged if, within ± 7 days of the onset of an AST or ALT elevation > 3 -fold ULN (including events which start or are ongoing through this interval), at least one of the following TEAE terms (excluding PT terms on the secondary path) is observed:

- ADAE.AEHLT = "Gastrointestinal and abdominal pains (excl oral and throat)";
- ADAE.AEDECOD in ("Vomiting", "Fatigue", "Nausea", "Pyrexia")
- ADAE.CQ16NAM = "Skin Rash (BicMQ narrow)"

An occurrence is also flagged if a $>5\%$ proportion in the ratio of eosinophils to total white blood cells is observed in the same sample as the detected AST/ALT elevation.

Clinically relevant findings in laboratory data will be reported as baseline conditions (at screening) or as AEs (during the trial) if judged clinically relevant by the investigator, and will be analysed as such.

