13. All patients completing week 12 of the study will be offered to enter open label trial 1368-0017. These patients are not requested to complete follow up period and will have their End of study visit at visit V6, co-inciding with the BL visit and start of study drug administration in 1368-0017.
14. EoS visit will be at week 12 (V6) for patients rolling-over into open label trial 1368-0017; and at week 24 for patients who will not enter open label trial 1368-0017.

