#### 5.2.6.2 Adverse event collection and reporting

##### **AE Collection**

[figure not shown]
The investigator shall maintain and keep detailed records of all AEs in the patient files. The following must be collected and documented on the appropriate CRF(s) by the investigator:

- From signing the informed consent onwards until the first dose of trial medication in the extension trial:
    - all AEs (non-serious and serious) and all AESIs.
  - For patients not rolling over into subsequent open label extension studies:
    - from signing the informed consent onwards until the individual patient's end of trial( including 16 weeks follow-up visit after last treatment dose) :
    - all AEs ( non-serious and serious) and all AESIs.
- After the individual patient's end of the trial:  
the Investigator does not need to actively monitor the patient for AEs but should only report any occurrence of cancer and trial treatment related SAEs and trial treatment

related AESIs of which the Investigator may become aware of by any means of communication, e.g. phone call. Those AEs should be reported on the BI SAE form, but not on the CRF.

Figure 5.2.6.2: 1 Adverse event collection and reporting

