6. GENERAL ANALYSIS DEFINITIONS

6.1 TREATMENTS

The trial comprises two distinct parts with different objectives. Patients in Part 1 will receive treatment with either BI 655130 300 mg i.v. single dose (SD), BI 655130 450 mg i.v. q4w, BI 655130 1200 mg i.v. q4w, or matching placebo.

For more details of study information on the treatment to be administered, assignment to treatment, and selection of dose, refer to Section 4 of the CTP.

The following study phases for Part 1 are defined:

Table 6.1: 1 Flow chart of analysis phases

Study analysis phase	Description	Start (included)	End (included)
Screening phase	Screening	Earliest of (Date of informed consent, first screening procedure)	Date/time of start of infusion of first study drug minus 1 minute.
Treatment phase & Residual effects period	On-treatment period	Date/time of start of infusion of first study drug (Day 1)	Patient dosed in extension: Date/time of first dose in extension – 1 minute ² . Patient not dosed in extension: Date of end of infusion of last study drug + 112 days at 11:59 p.m.
Follow-up ¹ phase	Off-treatment period	Date of end of infusion of last study drug + 113 days at 12:00 a.m.	Latest of: i) Date of EOS visit; ii) last contact date on End of Study page at 11:59 p.m.

Dates are defined individually per patient. If more than one date is associated with a specific visit, measurements associated with a specific date are assigned to a study analysis phase according to the rules specified in the table. An analysis phase will not extend beyond the start date of the following phase.

¹ The off-treatment period (i.e. Follow-up phase) only exists if the last contact date is after the date of end of last infusion + 112 days; does not apply to patients who roll over into the extension trial.

² Applies only to patients in the parent trial who are dosed in the extension trial. It is expected that roll over will occur within 2 weeks of the EoT visit in the parent trial, therefore, REP should not be applicable for definition of the on-treatment period. Note that for adverse event, where date and time are collected, events which occur on the same day of first dose in the extension, but prior to this administration are assigned to, and reported as a part of, the parent trial.

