6.7 BASELINE, TIME WINDOWS AND CALCULATED VISITS

Measurements reported with date and time and taken prior to start of administration of trial treatment will be considered pre-treatment values. Measurements reported with a date only (and no time) and taken on the day of first administration of trial treatment will also be considered pre-treatment values. These pre-treatment values will be assigned to visits according to the nominal visit number as recorded on the eCRF or as provided by the laboratory.

In addition, treatment-emergent adverse events which are reported with a date only (and no time) and which occur on the day preceding the first administration of trial treatment in the subsequent extension trial will be considered treatment-emergent AE in this parent trial.

Baseline, unless otherwise specified, is defined as the last measurement collected prior to the start of administration of the trial treatment.

Measurements taken after start of administration of trial treatment will be considered either on- or off-treatment values based on the definition in [Section 6.1](#), and will be assigned to visits for statistical analysis, if applicable, as defined below ([Table 6.7: 1](#)).

Analysis of AE data, concomitant medication or non-drug therapies, as well as use of rescue medication will not be based on visits. Therefore, no assignment to time windows will be necessary. Frequency tables for these data will be using on-treatment data only.

For derivation of the last value on treatment, minimum value on treatment, and maximum value on treatment, all on-treatment values (whether or not selected in any time window; see [Table 6.1: 1](#) for definition of the on-treatment period) will be considered; these will be derived for analysis of laboratory and vital signs data. For identification of potentially clinically significant abnormal laboratory values, all values (whether or not selected in any time window) within the on-treatment period will be considered.

Safety, efficacy and biomarker measurements will be assigned to visits based on extended time windows around the planned visit dates, defined relative to the day of first trial treatment (which is scheduled for Visit V2). These extended time windows are defined below in [Table 6.7: 1](#).

Table 6.7: 1 Time windows for assignment of efficacy, safety lab, vital signs and biomarker to visits for statistical analysis

Visit number /name	Visit label	Planned day	Time window (Days)				

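### The SAP contradicts itself on whether AE start time is collected, so adverse events before dosing on the roll-over day are in the treatment-emergent tables under one section and out under another

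*SAP*

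**What the plan says.** **SAP 6.1, Table 6.1:1.** For patients dosed in the extension, the on-treatment period ends at "Date/time of first dose in extension – 1 minute". Footnote 2 adds: "Note that for adverse event, where date and time are collected, events which occur on the same day of first dose in the extension", and continues "but prior to this administration are assigned to, and reported as a part of, the parent trial".

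**SAP 7.8.1.** The opposite premise appears here: "Since only the start date of an AE is collected (without start time"). The roll-over rule follows from it: "any AE which occurs up to one day prior to this first dose of extension trial medication will also be assigned to the on-treatment period". The exposure-adjusted rate in the same section censors event-free patients who were dosed in the extension at the date of that dose minus 1 day.

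**SAP 6.7.** For AEs reported without a time, it counts as treatment-emergent in this trial those "which occur on the day preceding the first administration of trial treatment in the subsequent extension trial". It does not say what happens to a date-only AE on the dosing day itself.

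**Protocol.** Section 5.2.6.2 collects all AEs in this trial's CRF "From signing the informed consent onwards until the first dose of trial medication in the extension trial". Section 7.3.5 treats as treatment-emergent any AE from start of treatment to the end of the residual effect period, 16 weeks after the last dose, with no exception for the roll-over day. Footnote 13 to the Part 1 flow chart places end of study at V6, "co-inciding with the BL visit and start of study drug administration in 1368-0017".

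**The concern.** The treatment-emergent flag drives the main AE tables. Two programmers working from different SAP sections would set it differently for an AE that starts on the day of the first extension dose but before it.

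By protocol plan that day is V6. It carries the only scheduled post-baseline sigmoidoscopy, with two sets of three biopsies (Protocol 5.5), done before study drug is given (Protocol 6.2.2). The risk table in Protocol 1.4 lists bleeding and perforation for this procedure. The disputed day is therefore one on which a recognisable type of AE could arise. SAP Section 7 expects most patients to roll over at Week 12, so rolling over is the usual path.

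What is at stake is whether those events appear in this trial's summaries, and whether the numerator and denominator of the exposure-adjusted rates cover the same days.

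**Working it through.** The plan gives no figure to reproduce. The check applies each rule to one example.

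**Inputs**
- First treatment is Day 1, V5 is planned for Day 57 and V6 for Day 85 (SAP Table 6.7:1).
- The residual effect period is 16 weeks, or 112 days (Protocol 7.3.5; SAP Table 6.1:1).
- Time at risk with an event is onset date minus start date plus 1 (SAP 7.8.1).
- Assumed for illustration: V6 and the first extension dose are both on Day 85, the dose is at 14:00, and an AE starts at 11:00 after sigmoidoscopy.

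**Step 1: the protocol's own definitions.** The AE precedes the first extension dose, so it is collected in this trial. With a last dose on Day 57, the residual effect period runs to Day 57 + 112 = Day 169. Even after a single dose on Day 1 it runs to Day 113. Day 85 lies inside both, so the AE is treatment-emergent by protocol.

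**Step 2: the SAP rules side by side**

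| SAP place | AE start time | Last moment assigned to this trial | AE at 11:00 on Day 85 |
|---|---|---|---|
| Table 6.1:1, footnote 2 | collected | Day 85, 13:59 | counted |
| 7.8.1, roll-over rule | not collected | end of Day 84 | not counted |
| 6.7 | date-only case | Day 84 named, Day 85 not mentioned | undefined |

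Section 7.8.1 does not exclude the dosing day in so many words. Its cut-off at the day before, together with censoring at dose date minus 1 day, leaves no other working reading.

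**Step 3: time at risk.** For an event-free patient dosed in the extension on Day 85, the censoring candidates are Day 84 (extension dose minus 1 day), Day 169 (last dose plus 112 days) and Day 99 (assuming no earlier data cut-off). The minimum is Day 84, which gives 84 days. If footnote 2 is followed, a patient with the Day 85 event contributes 85 − 1 + 1 = 85 days. The numerator then accepts events from a day that event-free patients' time at risk leaves out. The denominator effect is 1/85 = 1.2% per such patient.

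**Step 4: reach.** Footnote 2 to Table 6.1:1 expects roll-over within 2 weeks of the end-of-treatment visit, so dosing need not fall on V6. If it falls on a later date, V6 events count under both rules and the disputed day is that later date. The V6 endoscopy day is affected only in patients dosed on the V6 date, and no document gives their number.

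**The case against.** **Conditional reading.** The strongest reply is that footnote 2 applies only where a time happens to be recorded. Section 6.7 then supplies the date-only branch, and only one sentence of 7.8.1 is out of line. This is a fair reading of 6.1 and 6.7 together, and 6.7 cannot be cited as agreeing with 7.8.1 about the dosing day. It does not remove the conflict. If 7.8.1 is right that no start time exists, the same-day rule in footnote 2 can never operate. If a time does exist, the premise of 7.8.1 is false. Protocol 8.3.1 names AE onset date as mandatory and names no onset time, so the date-only case may be the real one, and for that case 6.7 leaves the dosing day undefined.

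**Unseen material.** The SAP refers to an ADS Plan and to sponsor AE-handling guidance. These may settle the programming, but their content is unknown and they would not correct the SAP text.

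**Small consequences.** This stands. All individual values are listed (SAP Section 7, General Remarks), serious AEs and AESIs go to the sponsor within 24 hours (Protocol 5.2.6.2), and no hypothesis is tested on AEs (SAP 7.8).

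**Stronger readings that the documents do not support**
- A reader might infer that the placebo comparison is distorted. The roll-over rule and the V6 schedule are the same in every arm, and nothing in the documents shows that roll-over-day events would differ by arm. The supportable effect is slight under-counting.
- A reader might infer that these events vanish from both trials, or reappear under open-label drug in 1368-0017. That depends on the AE rules of 1368-0017, which are not in these documents.
- A reader might see the same error at the start of treatment, because Table 6.1:1 cuts at the minute before infusion while 7.8.1 takes the whole first-dose day. The latter is an AE-specific convention with its reason stated, and it need not change if no time is collected.

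**Conclusion.** The contradiction is real and follows from the SAP text alone. Two sections disagree on whether AE start time exists, and they classify pre-dose AEs on the roll-over day differently. Following 7.8.1 leaves out of the treatment-emergent summaries events that the protocol collects here and defines as treatment-emergent. Following footnote 2 keeps them but mismatches the event-free time at risk.

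The size is modest: one day in about 85, or 1.2% of time at risk, for patients first dosed in the extension on the planned V6 day. How many AEs are involved cannot be estimated, because neither the number of same-day roll-overs nor an AE rate for that day is given. The endoscopy argument rests on the protocol's plan that V6 and the first extension dose coincide. No error rate or efficacy conclusion is touched. It merits correction because the day is the scheduled endoscopy day and the change is cheap.

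**What to change.** State once in the SAP whether AE start time is collected, and align four places with it: Table 6.1:1 with footnote 2, Section 6.7, the roll-over rule in 7.8.1, and the time-at-risk formula in 7.8.1.

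- An AE that starts on the day of the first extension dose belongs to this trial if it began before that dose. Decide this by start time if collected. Otherwise decide it by whether the AE is recorded in this trial's CRF, which matches the collection period in Protocol 5.2.6.2.
- End event-free time at risk on the day of the first extension dose, not the day before. In the example, patients with and without the event then both contribute 85 days.
- If no start time is collected, keep the whole-day on-treatment rule for the first-dose day. The CRF criterion cannot replace it there, because AEs enter this trial's CRF from consent onwards.

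The cost is SAP wording and one derivation in the AE dataset, with no new data. The downside is that a few more AEs appear in this trial's tables.
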